#### 7. Trial design

#### 7.1 Overall Design

This study is a Phase II, randomised, double blind, placebo controlled, multi-centre trial. We aim to recruit 200 patients presenting with stage II/III colorectal cancer.. Patients who consent to enter the study will receive the trial intervention for 2 weeks prior to their planned surgery and then be followed up for 5 years following surgery.

A master randomisation list generated by the Sponsor representative was made available at the start of the study. The master randomisation list is further divided into blocks of 20 and provided to each study site with the IMP deliveries. The Research Pharmacy or CRC at each site will retain the randomisation list upon receipt in their Pharmacy Site File. Upon receipt of a NeoART prescription the next sequential allocation will indicate whether to dispense active artesunate or matched placebo tablets to a particular participant. At the time of

dispensing the tear off label identifying the product will be removed by the Research Pharmacy or CRC and added to the accountability log. This will ensure that the investigators and study participants remain blinded to the treatment allocation. In exceptional circumstances, when knowledge of the investigational drug is essential for medical treatment of the patient, treatment allocation can be unmasked by pharmacy or CRC centres by a study coordinator that is not involved in the study directly .

The Sponsor retain a copy of the master randomisation list in their respective study files.

# 7.2 Schematic design of trial: Stage II/III Colorectal cancer planned for curative surgery

Day 0	Patient screening, consent, treatment allocation
Day 1	Artesunate 200mg PO OD 14 days or Placebo PO OD 14 days
Day 7	Midpoint telephone review
Day 14	
Day 14	End of treatment telephone review
Day 15	
	Safety blood test check prior to Surgery
	(Day 14/Day 15)
	Radical Surgery
Day 28	
	Blood test Check
Day 42	
	Post-Surgical Review
Month 6-60	
	Clinical follow up every 6 months for 5 years

# 8. IMP Dosage regimen and rationale

The dose of artesunate for the study will be 200 mg per oral (PO) once daily (OD) for fourteen days. There are no data on the most appropriate dose of artesunate in cancer in humans. This dose has been chosen by a consensus among medical experts experienced with using artesunate for the treatment of malaria and following published results from a pilot feasibility and safety study of neodajuvant oral artesunate in patients with colorectal cancer (Krishna et al. 2015).

The daily dose of artesunate used in combination treatments to treat uncomplicated Plasmodium falciparum malaria is 4 mg/kg, given over three days. When given as monotherapy for uncomplicated falciparum malaria the total dose is approximately 20 mg/kg, over seven to ten days. For curative courses in severe malaria, the total doses of artesunate (parenteral and oral combined) can reach 24 mg/kg. The daily dose of artesunate for a patient in this study will be between 2 mg/kg and 4 mg/kg, depending on the weight of the participant (ranging between 52-110 kg). At daily doses of 6 mg/kg the dose limiting side effect of artesunate is neutropenia. The study products do not contain porcine but contains produced from bovine that is safe for human consumption.

#### Metabolite

Artesunate is extensively hydrolysed by plasma esterases and possibly CYP2A6. Its main metabolite, DHA is metabolised through glucuronidation (WHOPAR., 2011).

#### Elimination

The plasma half-life of artesunate is 3-29 minutes whilst its active metabolite DHA has a plasma half-life of 40 to 95 minutes (WHOPAR., 2011).

If vomiting occurs during the course of treatment and the tablet is visible in vomit, the dose should not be retaken. The occurrence and frequency of any vomiting during the reporting period must be noted in the adverse events log and CRF.

#### The effect of food

The effect of food consumption with artesunate has been studied. When healthy volunteers consumed artesunate fixed dose combinations with a high fat meal, the Cmax and AUC (0-t) of artesunate decreased by 66% and 13% respectively, compared to fasting. The Cmax and AUC (0-t) of the active metabolite dihydroartemisinin (DHA) decreased by 48% and 5% respectively with a high-fat meal, compared to fasting (WHOPAR., 2011). Patients should take the study medication after a light meal.

#### Packaging and storage conditions

Study medication will be provided in bottles. One patient bottle will provide 28 tablets – sufficient for the duration of the study. The product labelling will be fully compliant with both Appendix E: Labelling Requirements of the Rules and guidance for Malaysian-Guideline-for-Application-of-CTIL-and-CTX-7.1-Edition and the protocol submitted and authorised by the NPRA.

Drug interactions with artesunate

There are no reports of negative drug interactions with artesunate to date.

Adverse events associated with artesunate

Artesunate is a safe drug that has been taken by millions of patients worldwide. In data taken from studies of malaria, serious side-effects are extremely rare.

The Summary of Product Characteristics for Artesunate provided to sites lists the potential side effects.

The reference safety information document provided to sites lists the adverse events considered by the Sponsor as being 'expected'.

#### Pregnancy

Artesunate is teratogenic in animal models and is contraindicated in the first trimester of pregnancy in humans. Pregnant women with malaria nevertheless are exposed to artesunate when no alternatives are available for treatment and studies published to date do not indicate an increased risk of teratogenicity. Pregnant women will not be recruited and participants will be required to use effective methods of medical contraception during the study. Women of child bearing age will be required to undergo a pregnancy test within 72 hours prior to commencing the study and must consent to adequate contraceptive methods from the time of consent and for up to 6 weeks following the end of treatment. Male participants with a partner of childbearing potential must agree to use adequate, medically approved contraceptive precautions from the time study consent is signed till up to 6 weeks after the last dose of study treatment intervention. Methods of contraception that are acceptable for the trial include the following:

The implant, the coil and male or female sterilisation will be acceptable for the trial. The injection and most forms of hormonal contraception will also be deemed acceptable for the trial if used in combination with condoms or other barrier methods. However, condoms alone won't be sufficient during the study.

IMPs and non-IMPs used in the trial

Patients entered into the study will be randomised to receive artesunate 200 mg (administered as 2 x 100mg tablets) or identical matching placebo once a day orally for 14 days.

Dosage modifications

No dosage modifications will be undertaken. Any Grade 3/4 reaction (according to Common Terminology Criteria for Adverse Events (CTCAE) Version 5.0) which occurs in any patient and is deemed related to the IMP or placebo by the treating investigator will result in that patient's trial treatment being discontinued.

#### 8.1 Source of IMPs including placebo

Bulk artesunate 100 mg and matching placebo tablets are manufactured by HCM- Medical

according to Good Manufacturing Practice (GMP). The matching placebo tablets contain lactose monohydrate, microcrystalline cellulose, croscarmellose sodium, colloidal anhydrous silica and a magnesium stearate blend.

Artesunate and placebo tablets are packaged into bottles each containing 28 tablets of either artesunate or placebo. Package labelling was performed under controlled conditions to ensure no cross contamination. The bottles have a removable label affixed. The removable label will allow identification of each bottle to facilitate correct treatment allocation in accordance with the randomisation list held in the pharmacy or clinical research centre departments. The pharmacy department or research centre will remove the labels during the dispensing process and affix all of the labels to the IMP accountability records.

The named Qualified Person (QP) will issue a QP release certificate. The IMP will be delivered, accompanied by the QP batch release certificate.

Shipment of the IMP will be under temperature-controlled conditions and the recipient pharmacy department at each site will be required to confirm by return of a completed delivery note as instructed that correct shipment conditions have been maintained. A copy of the QP release will be provided to each site to file in the Pharmacy Site File (PSF).

Full IMP accountability will be maintained at all participating site pharmacy departments.

Temperature records are to be maintained with daily minimum/maximum readings via a calibrated/certificated thermometer. The records will be available for monitoring visit purposes and either a copy of those records or a signed statement of compliance will be placed in the PSF following the end of IMP treatment phase.

The IMP – artesunate/placebo 100 mg tablets must be stored below 25°C.

#### 8.2 Accountability procedures for the IMP(s)

Each participating site's pharmacy department will be responsible for maintaining and updating the IMP Accountability Log, filed in the pharmacy site file. All used/unused IMP(s) will be returned to the site pharmacy. If research pharmacy is not available at the study site, a qualitfied study coordinator that is not part of the investigator's team can perform this task.

IMP(s) destruction will be conducted, following verification by the Clinical Trials Monitor and agreement by the Sponsor, in accordance with local pharmacy practice. Destruction records will be maintained and filed in the site pharmacy site file.

#### 8.3 Assessment of compliance

An assessment of medication compliance will be made by the principal investigator or delegated research team, member on Day 7 and at the end of the treatment course based on verbal answers given to direct questioning and a count of untaken medication on Day 15. These data will be entered into the Case Report Form.

Following completion of the patient's IMP treatment period any unused medication will be returned to the site Pharmacy department for the IMP accountability log to be updated. Patients who take the study drug for < 8 days in the 14 day treatment period will be considered 'non-compliant'. All patients will continue to be followed up according to the study protocol regardless of compliance.

#### 8.4 Post-trial IMP arrangements

This is a neoadjuvant study. There will be no further IMP supplied to participants following colorectal surgery.

## 8.5 Name and description of each non-IMP (NIMP)

No NIMPs used.

#### 8.6 Concomitant treatment

There are no reports of negative drug interactions with artesunate to date. Concomitant medication details will be collected at baseline and any changes recorded at subsequent study visits.

We will document adjuvant treatment following surgery such as chemotherapy and aspirin therapy. We will include this in our final data analysis in order to account for any confounding results that could arise as a result of adjuvant therapy. If patients develop Grade 3 neutropenia or more (according to the Common Terminology Criteria for Adverse Events (CTCAE) Version 5.0) Definition of neutropenia: A disorder characterized by an ANC <1000/mm3 and a single temperature of >38.3 degrees C (101 degrees F) or a sustained temperature of >=38 degrees C (100.4 degrees F) for more than one hour. Grade 3 neutropenia: ANC <1000/mm3 with a single temperature of >38.3 degree C (101 degrees F) or a sustained temperature of >=38 degrees C (100.4. degrees F) for more than one hour. They should be managed with granulocyte colony stimulating factor (GCSF) supplied via routine hospital pharmacy in accordance with local policy and prescribing practice.

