# 4. Primary Objective

The primary objective of the study is to determine if neoadjuvant oral artesunate improves progression free survival at 2 years in Stage II/III colorectal cancer compared to standard treatment with surgery alone +/-adjuvant post-operative chemotherapy where indicated.

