#### 6.11 Study Rationale and risk/benefit analysis

Neoadjuvant pre-operative chemotherapy is effective in a number of other cancer types supporting the theory that optimal neoadjuvant systemic therapy at the earliest opportunity may be more effective at eradicating distant metastases compared to adjuvant therapy delivered following the delay and immunological stress of surgery. Colorectal cancer metastases have a short doubling time (Tanaka *et al.*, 2004; Finlay *et al.*, 1988) and it has been postulated that micrometastatic tumour growth may be further accelerated in the early post operative period by enhanced growth factor activity (Zeamari *et al.*, 2004; Fahmy *et al.*, 2003; Schelfhout *et al.*, 2002). Neoadjuvant therapy also confers the potential advantage of primary tumour shrinkage, thereby reducing the risk of incomplete surgical excision and tumour shedding contaminating the surgical field during surgery (Nelson *et al.*, 2001). This may have particular relevance for transcoeliac spread with peritoneal metastases found in up to 50% of patients with locoregional relapse (Assersohn *et al.*, 1999). Neoadjuvant preoperative therapy in colorectal cancer started within days of diagnostic and staging investigations provides an unique treatment paradigm that could potentially eradicate micrometastases not managed with current standard treatment regimes.

Indeed, neoadjuvant combination chemotherapy with or wothout targeted anti- EGFR monoclonal antibody therapy with panitumumab forms the basis of the current FOxTROT trial (FOxTROT Collaborative Group., 2012). As previously mentioned however these regimens are associated with significant toxicities and surgery is often delayed whilst patients recover from these effects. These treatments are also expensive and remain economically out of reach for the majority of patients in developing countries.

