#### 17.2 Endpoints

## 17.2.1 Primary endpoints

The primary endpoint for the main comparison between the artesunate treatment and placebo arms will be persistent disease or disease recurrence, two years following surgery. All analyses will be made on an intention to treat basis, although per protocol analyses will also be reported. Statistical significance will be assumed at the 5% level unless otherwise indicated.

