#### 17.2.2 Secondary endpoints

Secondary endpoints will include:

- Overall survival at 2 and 5 years
- Recurrence free survival at 5 years
- Colon cancer specific death at 2 and 5 years
- Artesunate drug related toxicity
- Adverse events
- Pathological assessment of tumour regression (involvement of lymph nodes; serosa; resection margin)
- Quality of life (EuroQol EQ-5D, EORTC QLQ C-30, EORTC QLQ-CR29)
- Surgical morbidity/mortality
- Predictive value of tumour biomarkers in terms of predicting response to artesunate therapy
- Biomarker and molecular profiling studies

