# 17.3 Sample size and recruitment

#### 17.3.1 Sample size calculation

We performed our sample size calculation largely based on inferences drawn from our pilot Phase I study (Krishna *et al.*, 2015). The input assumes that the analysis would be conducted using a univariate Cox proportional hazard survival model from the time of surgery to the first disease recurrence with one binary covariate representing treatment groups (artesunate or placebo). We calculated that a minimum sample size of 168 patients is necessary to test a hazard ratio (HR) of 0.56 for the intervention versus placebo. This value is within the confidence intervals estimated in our phase I study (Krishna *et al.*, 2015) and somewhat between the point estimate in the worse case scenario inference in the paper and a value of 0.7 commonly circulated in oncology clinical trials. For this Phase II study, we set the power at 0.8 and accepted a type one error of 0.1 for a one-sided test.

- 1) The null nypothesis H0: HR=0.56 (equivalent ≤)
- 2) The alternative hypothesis H1: HR>0.56

These settings would result in a sample size of 168 patients. Inflating this sample size by 15-20% to allow for loss at follow-up would result in approximately 194-202 patients. We believe that 200 patients therefor represents a feasible and achievable target given our time and financial constraints.

The rationale and sensitivity analyses for these calculations are outlined below. The general setting is that of a survival analysis where the event is defined as the first disease recurrence after surgery.

A cohort of Stage II/III colorectal cancer patients undergoing surgery will be randomised as per recruitment to receive the artesunate intervention or placebo. Patients will be followed-up for 5 years following surgery. The minimum sample size to test a hazard ratio (HR) of 0.56 for the intervention vs. placebo group is based on:

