#### Calculation framework:

- 1. The minimum sample size calculation has been calculated as for a univariate Cox proportional hazard survival model with one binary covariate representing treatment groups (artesunate or placebo).
- 2. The necessary number of events are calculated as

[figure not shown]
$$D = (Z_{1-\alpha} + Z_{1-\beta})^{2} \left[ P \times (1 - P) \times (\log(HR))^{2} \right]^{-1}$$

Where P represents the proportion of the sample assigned to the treatment group (0.5 corresponding to a 1:1 treatment assignment in our setting) and the HR is the estimated hazard ratio of the event (disease recurrence) for the treatment group vs. placebo. The values of the inverse of the standard normal cumulative distribution function are

 $Z_{1-\alpha}=1.28$  for one sided  $\alpha$ =0.1 and  $Z_{1-\beta}=0.842$  for  $\beta$ =0.20 (equivalent to 80% power).

3. Hence, the minimum total number needed for the trial is calculated as

$$N = D \times (100/32)$$

Graph 1: Study sample size- a sensitivity analysis to various settings for hazard ratios and type one error for one-sided test.

Total number	One sided level of	HR	Number of events
participants	significance		
53	.15	4	17
56	.15	.4 .41	18
59	.15	.41	19
62	.15	.42	20
66	.15	.43	22
70	.15	.45	23
74	.15	.46	24
78	.15	.47	25
82	.15	.48	27
87	.15	.49	28
92	.15	.5	30
104	.15	.52	34
117	.15	.54	38
132	.15	.56	43
149	.15	.58	48
169	.15	.6	55
193	.15	.62	62
222	.15	.64	72
256	.15	.66	82
297	.15	.68	96
347	.15	.7	112
68	.1	.4	22
71	.1	.41	23
75	.1	.42	24
80	.1	.43	26
84	.1	.44	27
89	.1	.45	29
94	.1	.46	31
99	.1	.47	32
105	.1	.48	34
111	.1	.49	36
118	.1	.5	38
132	.1	.52	43
149	.1	.54	48
168	.1	.56	54
190	.1	.58	61
216	.1	.6	70
247	.1	.62	80
283	.1	.64	91
327	.1	.66	105
379	.1	.68	122
443	.1	.7	142
93	.05	.4	30
98	.05	.41	32
103	.05	.42	33
109	.05	.43	35
115	.05	.44	37
122	.05	.45	40
129	.05	.46	42
136 144	.05	.47	44
152	.05	.48 .49	47 49
	.05 .05	.5	52
161			
181	.05	.52	58
204	.05 .05	.54	66 74
230		.56	
261	.05 .05	.58	84
207	U.S.	.6	96
297			100
339	.05	.62	109
			109 125 144

608	.05	.7	195

Table 2: Details sensitivity analyses to various settings for hazard ratio values. Power is set at 0.8.

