# 17.3.3 Statistical analysis plan

The event of interest (failure defined as cancer recurrence from a survival analysis perspective) is defined as the first recurrence of the disease after the patients' treatment allocation and surgery. Patients will be followed-up for 2 years; if the event of interest does not occur the patient will be considered (right) censored. The general assumption for time-to-event (survival analysis) is that the censoring is non-informative, i.e. it is independent of the event process. The Cox proportional hazard (PH) model would be applied to investigate the hazard ratio of disease recurrence for the artesunate group versus placebo group. The semi-parametric technique allows no assumption to be made on the baseline hazard; nevertheless proportionality of the hazards in the two arms should hold. The latter assumption can be tested on the basis of Shoenfeld residuals after fitting the model to the data.

We discussed an interim analysis in December 2021 with the DMC and TSC. At this time point 78 patients will have reached the primary end point (recurrence free survival 2 years after surgery). This analysis will be performed by an independent trial statistician familiar with both trials ([name]) and a report presented to the DMC and TSC members for review and recommendations thereafter.

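### Section 8.6 puts post-surgical adjuvant therapy into the final analysis to remove confounding, but therapy begun after randomisation cannot confound the arms

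*Protocol*

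**What the plan says.** Section 8.6 states that chemotherapy and aspirin given after surgery will be documented, and continues: "We will include this in our final data analysis in order to account for any confounding results". It does not say which analysis is meant, in what form the therapy enters, or whether that analysis is primary or supportive. The same section records concomitant medication at baseline.

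Other parts of the protocol bear on this:

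- Section 4 defines the comparison as artesunate "compared to standard treatment with surgery alone +/-adjuvant post-operative chemotherapy where indicated".
- Section 17.2.1 sets the analysis principle: "All analyses will be made on an intention to treat basis, although per protocol analyses will also be reported".
- Section 17.3.1 sizes the trial on a model with arm alone: "The input assumes that the analysis would be conducted using a univariate Cox proportional hazard survival model". Its calculation framework repeats this: "univariate Cox proportional hazard survival model with one binary covariate representing treatment groups (artesunate or placebo").
- Section 17.3.3 describes the primary analysis by arm: "The Cox proportional hazard (PH) model would be applied to investigate the hazard ratio of disease recurrence for the artesunate group versus placebo group". No adjuvant-therapy covariate is listed there or elsewhere in Section 17.

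**The concern.** A confounder of a treatment comparison has to influence, or share a cause with, who receives which treatment. Here allocation is random and comes before surgery, whereas adjuvant therapy comes after it. Differences between arms in adjuvant use are therefore either chance or a consequence of allocation. Neither is confounding, so the purpose given in Section 8.6 does not apply to the comparison of arms.

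A consequence of allocation is plausible from the protocol itself. Section 6.11 argues: "Neoadjuvant therapy also confers the potential advantage of primary tumour shrinkage, thereby reducing the risk of incomplete surgical excision". Section 17.2.2 makes the relevant pathology an endpoint: "Pathological assessment of tumour regression (involvement of lymph nodes; serosa; resection margin"). Section 6.1 ties the benefit of postoperative chemotherapy to stage III and some stage II disease. If artesunate changes the pathology, it can change who receives chemotherapy. No passage puts a figure on this, so the path is plausible but not documented.

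What is at stake is the meaning of the primary hazard ratio. Adjusted for adjuvant therapy, it would no longer be the effect of being assigned artesunate under the strategy in Section 4. With the choice left open, two different hazard ratios could each be defended after the data are seen.

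**Working it through.** **1. Order of events.** Randomisation is 1:1 (Section 11.2). Study drug starts fifteen days before surgery and ends the day before it (Section 12.3). Adjuvant therapy follows surgery (Section 8.6). The order is allocation, study drug, surgery and pathology, then adjuvant therapy, so the last cannot influence the first. Aspirin already taken at entry is different: it is a baseline variable.

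**2. The plan's own figure.** Section 17.3.1 gives 54 events and 168 patients for HR 0.56, one-sided alpha 0.10, power 0.80, half the patients in each arm and 32% with events:

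- D = (1.2816 + 0.8416)² / (0.25 × ln(0.56)²) = 53.6, so 54 events.
- N = 53.6 × 100/32 = 167.6, so 168 patients.

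The figure reproduces. It belongs to a model with arm as the only covariate, and this point does not change it.

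**3. Size of the shift if Section 8.6 reached the primary model.** The protocol gives no adjuvant rates or effects, so every input in this step is an assumption:

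- Placebo node-positivity is 50%; artesunate node-positivity is 50, 45, 40 or 35%.
- Chemotherapy goes to 85% of node-positive and 20% of node-negative patients.
- Placebo 24-month risk is 40%.
- Times run from surgery, are exponential, and are censored at 24 months.
- Setting 1: nodal HR 4, chemotherapy HR 0.7, direct artesunate HR 0.65.
- Setting 2: nodal HR 1.5, chemotherapy HR 0.5, direct artesunate HR 0.56.

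Chemotherapy use is 0.85p + 0.20(1 − p), where p is node-positivity. That is 53% at p = 0.50, and 49%, 46% and 43% at p = 0.45, 0.40 and 0.35.

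Cox models were fitted to 2,000,000 simulated patients per scenario, by arm only and by arm plus chemotherapy. Log-HR shifts come from unrounded estimates.

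| Chemotherapy use, placebo vs artesunate | Setting 1: arm only, adjusted | Shift in log HR | Setting 2: arm only, adjusted | Shift in log HR |
|---|---|---|---|---|
| 53% vs 53% | 0.670, 0.666 | -0.006 | 0.561, 0.559 | -0.005 |
| 53% vs 49% | 0.630, 0.638 | +0.012 | 0.565, 0.554 | -0.019 |
| 53% vs 46% | 0.594, 0.612 | +0.029 | 0.568, 0.550 | -0.032 |
| 53% vs 43% | 0.561, 0.587 | +0.045 | 0.568, 0.542 | -0.047 |

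With equal use there is nothing to correct; the small residue is non-collapsibility of the hazard ratio. With unequal use the sign depends on whether the chemotherapy covariate mainly carries stage risk (Setting 1) or mainly carries benefit (Setting 2).

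A placebo risk of 34% instead of 40% gives nearly the same result at 53% vs 43%: 0.562 vs 0.588 in Setting 1 and 0.569 vs 0.544 in Setting 2.

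**4. Scale.** With 54 events split evenly, the standard error of the log HR is about √(4/54) = 0.27. The largest shift, 0.047, is about one sixth of that.

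**5. Power and verdicts.** These come from 4,000 simulated trials of 168 patients per scenario, with 54 to 58 events, at one-sided 0.10.

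| Setting | Use, placebo vs artesunate | Power, arm only | Power, adjusted | Trials with opposite verdicts |
|---|---|---|---|---|
| 1 | 53% vs 53% | 0.596 | 0.607 | 5.6% |
| 1 | 53% vs 49% | 0.658 | 0.646 | 5.3% |
| 1 | 53% vs 43% | 0.799 | 0.740 | 6.6% |
| 2 | 53% vs 53% | 0.802 | 0.802 | 3.2% |
| 2 | 53% vs 43% | 0.777 | 0.825 | 5.4% |

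If artesunate has no effect at all, the rejection rates are 0.097 and 0.099, so type I error is not affected.

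**6. The adjustment does not isolate the chemotherapy effect.** The fitted chemotherapy HR is 1.70 to 1.72 in Setting 1, where 0.7 was assumed, and 0.65 in Setting 2, where 0.5 was assumed. Patients given chemotherapy are those with worse stage, so the covariate carries stage risk.

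A further problem is not in these simulations. Chemotherapy starts after the time origin (surgery), so an ever/never covariate would also bring in immortal time.

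**7. A second set of assumptions.** Stage III is 50% on placebo, chemotherapy goes to 80% of stage III and 20% of stage II, and the direct HR is 0.7. With stage HR 3 and chemotherapy HR 0.7:

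- Equal use: 0.719 by arm only, 0.718 adjusted.
- Stage III lowered by 20 points, so use is 50% vs 38%: 0.597 and 0.617.

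The pattern is the same.

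**The case against.** The strongest reply is that Section 8.6 never mentions the primary estimate, the Cox model or the comparison of arms. The sections that govern the primary analysis describe a model by arm, so this is an ambiguity rather than a contradiction. How adjuvant data enter an analysis is normally settled in the statistical analysis plan, which is not shown. The sentence also has sound uses: per-protocol and biomarker analyses are not protected by randomisation, and accounting for adjuvant therapy there can be reasonable. A model with an extra covariate can still analyse every patient as randomised. Finally, the size is assumed throughout. The largest shift needs two weeks of artesunate to cut node-positivity from 50% to 35%, and even then the sign is not predictable.

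Much of this stands. The conflict with intention to treat is conditional on Section 8.6 reaching the primary estimate. What changes is the quantity estimated, not the set of patients analysed. The effect runs from nil to modest. The rate of opposite verdicts with unequal use (5 to 7%) should be read against 3 to 6% with equal use.

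It does not remove the point. The objection is to what the protocol states, not to a detail left for later. The sentence commits the final analysis without limit and gives a reason that fails for the randomised comparison, and nothing in Section 17 restricts it. An analysis plan that followed it literally would put a post-randomisation covariate into the final analysis; one that did not would depart from the protocol.

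**Conclusion.** The point holds. Section 8.6 is wrong as written for the comparison of arms: therapy begun after randomisation cannot confound it, and adjuvant chemotherapy is part of the strategies that Section 4 compares. If the sentence were applied to the primary estimate, the hazard ratio would no longer be the intention-to-treat effect, and the adjustment would not recover the chemotherapy effect either.

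The numerical consequence is about nil if artesunate leaves adjuvant use unchanged. It is modest, in either direction, if use differs by about 10 percentage points: at most about 0.05 on the log-HR scale and 5 to 6 points of power. These sizes depend wholly on assumed chemotherapy rates, nodal and chemotherapy effects, and an assumed effect of artesunate on nodal status. The conclusion about the stated reason depends only on the order of events. The sample size is unaffected.

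**What to change.** Replace the sentence in Section 8.6 with:

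> Adjuvant therapy after surgery will be summarised by arm. It will not be a covariate in the primary ITT treatment-effect model. Any analysis that uses it will be labelled supportive, with its estimand stated.

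This still allows per-protocol or biomarker analyses that use adjuvant therapy.

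Apply the same wording to the pooled analysis of the UK, Vietnam and Malaysia studies (Section 17.3.2). The other two protocols are not shown, so whether they carry the same sentence has to be checked. The cost is one replaced sentence and that agreement. No new data are needed, and adjuvant therapy is still collected and reported.
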